3.3 Additional Measures

- Program evaluation: We will evaluate the presentation with 7 investigator created items at T1 and 2 items at T2 for all patient-participants and an additional 5 items at T1 for those patients who viewed the personalized risk information. The items will measure satisfaction and usefulness of the presentation as well as the perceived trustworthiness of the information.
- Provider Intervention evaluation: We will evaluate the personalized message with an investigator created survey for all providers randomized to receive the screening reminder + personalized message. The items will measure how much the personalized information was helpful, how much they would use it if integrated into the electronic health record (EHR), what type of patient they would use the information
- *Impact of COVID-19 on screening preferences and intentions* (T2): will be assessed with one open-ended question: “How has the COVID-19 pandemic affected your decision about getting screened for colorectal cancer?” Patients also will be provided with a list of common factors affecting decisions from which they can check all that apply.
- *Reasons for test preference, test choice, and follow-up for discordance* (T2): Patients will answer an open-ended question about their intent to be screened and test preference. Patients whose screening intent or test choice changed from T1 will be asked to explain the reason for the change.

Providers: Data collection from providers will include:

- *Ordering of CRC screening test* will be assessed by reviewing the EHR for orders for FIT, colonoscopy, or other CRC screening test for each patient at six-month follow up.
- *Opening of provider notification* will be assessed for providers by reviewing the EHR.
- *Demographic data* (including age, gender, time in practice at enrollment) will be assessed using the AMA Physician Datafile.

4.0 Eligibility Criteria

4.1 Inclusion Criteria

Patients will be eligible if they are:

- age 50-75 years
- have not had colonoscopy performed in last 10 years, sigmoidoscopy in last 5 years, or fecal occult blood testing (FOBT or FIT) in the last year, or Cologuard in the last 3 years
 - have not had a colonoscopy since age 50 years
 - have a scheduled appointment with a provider who agreed to participate in the study and approved approaching their patients.

Providers will be eligible:

- if they are a physician (MD or DO), nurse practitioner (NP), or physician assistant (PA) practicing at one of our research sites

4.2 Exclusion Criteria

Patients will be excluded if they are:

- undergoing workup for symptoms consistent with CRC, such as unexplained weight loss, change in bowel habit, or rectal bleeding
- have a diagnosis or medical history conferring elevated risk for CRC including a previous adenomatous polyp or CRC, inflammatory bowel disease, high-risk syndromes, or a significant family history of CRC (two or more FDRs with CRC or one FDR with a CRC diagnosis prior to age 60)
 - are unable to speak and read English
 - previously participated in any research projects regarding colorectal cancer screening or colonoscopy including, but not limited to our previous studies.
 - Members of the study team will not be participating in the study; therefore, patients who have a scheduled appointment with any member of the study team will not be eligible.

Providers will be excluded if they are:

- None

5.0 Study Design

We will conduct a 2x2, randomized, controlled trial (**see Table 2**) to compare decision quality and screening uptake in four groups of patients who view a decision aid:

- Group 1) without the personalized message and whose providers do not receive the personalized message (control group)
- Group 2) with the personalized message and whose providers do not receive the personalized message;
- Group 3) without the personalized message and whose providers receive the personalized message, and
- Group 4) with the personalized message and whose providers receive the personalized message.

[figure not shown]
Table 2

Provider receives:	Patient views:	
	Decision aid WITHOUT personalized message	Decision aid WITH personalized message
Screening reminder	Group 1	Group 2
Screening reminder + Personalized message	Group 3	Group 4

We have chosen a 2x2 design in order to separately evaluate the impact of personalized messages provided to patients and to providers. It is essential to evaluate these two interventions separately due to the expense and effort required for implementing either of them. We will cluster patients by provider in order to avoid the danger that providers who received the message for some of their patients would use similar methods for patients for whom they did not receive the message.

Comparators: Our study involves three comparators: (1) a CRC screening decision aid without a personalized ACN risk message, (2) a CRC screening decision aid with a personalized ACN risk message, (3) A provider message with personalized ACN risk information.

Study Flow Diagram:

6.0 Enrollment/Randomization

Patients: We will recruit patients from primary care clinics from two healthcare systems in Central Indiana: the IU Health Physicians' primary care practices of the Indiana University Health system (currently 34) and the primary care practices of Eskenazi Health (currently 9). These clinics serve a wide range of socioeconomic groups, including rural, upper-income suburban, middle-income urban/suburban, and lower-income urban (including 7 Federally Qualified Health Centers). Nineteen of the IU Health practices are outside of Indianapolis, and 4 are > 40 miles from the academic health center. (PC-2)

Clinical Information Specialists at IU Health will identify potentially eligible patients who have an upcoming appointment using a query of their electronic health record (Cerner) and will share that list with the research team weekly or biweekly. Eskenazi Health's potentially eligible patients will be identified by the Regenstrief Data Core, also on a weekly or biweekly basis. Both health systems will save a list of potentially eligible patients, along with their medical record number (MRN), street address, phone number, upcoming clinic appointment date and healthcare provider, and EHR patient portal enrollment status in a secure server accessible by the project manager and data manager. These lists will be updated on a regular basis throughout the recruitment period.

The research team will send potentially eligible patients a letter of introduction explaining the study (see Notes & Attachments for letter and brochure). The letter will also include a phone number that patients can call to opt out of being contacted. A week later, the research assistant will call patients (see Notes & Attachments for phone script) who have not opted out to explain the study and answer questions about study requirements, potential risks, and compensation. If the patient is interested in joining, the research assistant will confirm eligibility. If the patient is eligible, the research assistant will review the study information sheet (SIS) and HIPAA authorization. The SIS and HIPAA authorization will be emailed to the participant after the recruitment call with instructions and encouragement to contact the study team with questions. If the patient prefers, the research assistant can schedule a follow-up call to discuss the SIS and HIPAA authorization after the patient has had time to receive and review. For those patients who refuse to be assessed for eligibility, the RA will record reasons for refusal.

Participants will be offered three options to access the decision aid and complete the first two surveys (T0 and T1). They may choose to receive an electronic link: (i) through the EHR patient portal (preferred), (ii) by email, or (iii) on an iPad provided at the patient's clinic. For systems (i) and (ii), the research assistant will provide assistance as needed by phone when the patient opens the link or in the clinic for those who wish to use the iPad (method iii).

The electronic link will take the patient to a Qualtrics database. A randomization scheme, generated by our Biostatistics team, will be connected to the Qualtrics database. When the participant enters Qualtrics, this will trigger Qualtrics to assign them to the Control group (view the non-personalized DA) or the Intervention group (View the personalized DA).

Research team members interacting with the participants will be blinded to patient assignment. The patients will be blinded to assignment of their provider.

Providers: The providers will be identified through each health system's provider directory, and confirmed and updated by the practice administrators. All eligible providers will be sent a letter and study information sheet explaining the study (see Notes & Attachments for letter and SIS), and be given the opportunity to let the research team know if they choose not to participate. Providers who agree to participate will be randomized to the Control group (receives a generic message) or the intervention

group (receives patient's ACN risk). The providers will be randomized based on a randomization scheme generated by our Biostatistics team.

The research team will not be blinded to provider assignment as they will need to know which notification to send. Providers will know that their patient enrolled in the study; however, the provider will be blinded to the patient's group assignment.

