- *Perceived Shared Decision Making* (T2) will be assessed with two measures. Patients will first answer five items adapted from the Shared Decision Making Process_4 Survey. This tool is a National Quality Foundation Measure used to assess the extent to which patients are involved in the decision-making process (PC-3, IR-4).⁵⁴ Patients will also respond to the 3-item CollaboRATE measure that assess three key areas of shared decision making; 1) explaining the health issue; 2)

asking for patient preferences; and 3) incorporating patient preferences into the decision. Each item uses likert response options ranging from “no effort was made” to “every effort was made”.^{73, 74}

- *Numeracy*: *Subjective numeracy* will be assessed at T0 with the Subjective Numeracy Scale (SNS) – short form, a validated instrument that involves 3 Likert-style questions.^{67, 71, 72}
- *Literacy* (T0) will be assessed using a 3-item health literacy scale (IR-4).⁷⁵
- *Demographic data* (T0) (including age, gender, income, education), as well as data on previous MD CRC screening recommendations, will be assessed utilizing a survey that has been used by our team and other researchers in multiple studies of CRC screening.^{51, 69}

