7.2 Data Collection

Patients: Potentially eligible patients will be sent a letter of introduction and explanation about the study. The letter will inform patients that they will receive a call about the study in the next few days and will include a telephone number to call if they wish no further contact. A week after letters are mailed, the research assistants will call patients who have not called the "opt out" number. The research assistants will explain the study and answer patients' questions about study requirements, potential risks, and compensation. If the patient is interested in joining, the research assistant will confirm eligibility. If the patient is eligible, the research assistant will review the study procedures, the informed consent document and HIPAA authorization, and obtain verbal consent and authorization.

The research assistant will then collect the data to calculate the participant's risk for having an advanced colorectal neoplasm (ACN). This involves confirming gender, age, and family history of colorectal cancer. The research assistant will ask the patient for their smoking history and calculate pack years (none, < 30 pack years; \geq 30 pack years). The research assistant will also ask the participant for their waist size (for men: under 37 $\frac{1}{2}$ in; 37 $\frac{1}{2}$ - 47 in; $>$ 47 in; and for women: < 34 $\frac{1}{2}$ in; 34 $\frac{1}{2}$ - 43 $\frac{1}{2}$ in; $>$ 43 in).

The research assistant will discuss with the participant which of the 3 options they prefer to access the decision aid and survey: (i) through the EHR patient portal, (ii) by email, or (iii) on a iPad at a primary care practice. Based on that discussion, the research assistant will send the participant the link to their survey and decision aid. The research assistant can be available by phone or in-person at the practice as needed to assist participants in accessing the survey and decision aids. The research assistant will encourage participants who choose to access the surveys and decision aid on their own device to do so in a quiet location free as possible from distractions.

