The email sent to participants will review the study procedures, who to contact with questions, and the unique link to their survey in Qualtrics. When the participant clicks the link, they will be taken to Qualtrics and the baseline survey (T0). After the participant completes T0, Qualtrics is programmed to stream the appropriate decision aid for that participant. When the decision aid completes, the post-intervention survey (T1) will display. Following completion of T1, the participant will be automatically sent a confirmatory email thanking them for completing this part of the study, reminding them of the next study contact, and who to contact with questions.

The baseline (T0) and post-intervention (T1) surveys are planned to take about 10 minutes each to complete. The control decision aid is approximately 10 minutes long and the intervention decision aid is approximately 15 minutes long (see Appendix for T0 and T1 surveys).

Research assistants will start contacting participants approximately four days after the participant's provider visit to complete the post-provider visit (T2) survey. Research assistants will aim to start collecting the T2 data four days after the provider visit; however, if the patient requests contact sooner due to scheduling conflicts, the research assistant will contact the patient as requested. Research assistants will first attempt to collect the T2 data over the phone; however, if unsuccessful or if the participant prefers, the research assistant can email the participant a link to complete the survey online in REDCap.

The post-provider visit (T2) survey is planned to take about 15 minutes (see Appendix for T2 survey).

Research assistants will start contacting participants 6 months after study enrollment to complete the 6-month follow-up (T3) survey. Research assistants will first attempt to collect the T3 data over the phone; however, if unsuccessful or if the participant prefers, the research assistant can email the participant a link to complete the survey online in REDCap.

The 6-month follow-up (T3) survey is planned to take about 15 minutes (see Appendix for T3 survey).

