Analytic plan: Preliminary analyses will compare baseline demographic information across the four groups using means and standard deviations for continuous variables and frequency distributions for categorical variables. We will adjust for those characteristics in subsequent analyses if significant differences emerge at a conservative level for inclusion of a covariate ($p<.20$). Characteristics of participants who don't complete T1 and/or T2 will be compared with those who remain to determine what biases may exist. The above analyses will be conducted using ANOVA, chi-square tests, or exact or non-parametric equivalents. If there appear to be biases in dropout, we will conduct pattern mixture models analyses to see how the results could change based on the missing data assumption (IR-5, MD-2, MD-3, MD-4). Primary analysis of outcomes will employ an intent-to-treat analysis. For Aim 1, our primary hypotheses will be tested using logistic regression models with the outcomes of informed choice and uptake (both yes/no outcomes) and main effects for: 1) patient receipt of personalized message; and 2) provider receipt of personalized message. A random effect for provider will be included to account for the clustered randomization. We will test for an interaction effect, but do not expect one so have not powered the study for an interactive effect. The secondary hypotheses (planned subgroup analyses with low risk group) will be tested using the same model type (HT-2, HT-3). The secondary hypotheses are considered exploratory. For Aim 2, mediation effects (RQ-6) will be estimated in a logistic regression setting, fitting the appropriate mediation models using MPlus⁷⁶ and then testing indirect effects using the percentile bootstrap approach to estimate the indirect effect.⁷⁷ For primary analyses, we will fit models that estimate the effects of either or both of the interventions relative to control. Moderators (RQ-4, HT-1, HT-2, HT-3, HT-4) will be identified by significant interaction terms in the regression models from Aim 1.

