Confidentiality will be maintained by assigning each participant a unique identification number and using this number to identify the participant on all data collection forms. We will keep all paper documents locked in lockable cabinets in a locked office suite. Most of the data will be entered directly into REDCap or Qualtrics, HIPAA-aligned web environments. Processes and procedures have been documented and implemented to ensure the security and protection of the data within the computer operations centers, the servers, and the databases. Only those study team members who need access to this information will be allowed by the PI or study coordinator. All participants will be fully informed about the study prior to enrollment and be given the opportunity to decline to answer any questions or to discuss any issues they find troubling. They will be told that they can terminate participation at any time for any reason.

Research team members will be trained in procedures to allow participant to withdraw from the study. REDCap and Qualtrics surveys will allow participants to pass over questions and still continue through the remainder of the questions.

All study team members including those involved with the recruitment, informed consent process, and data collection will be adequately trained. Training will include passing of our institution's required Collaborative Institutional Training Initiative (CITI) modules and ongoing study-specific training from study personnel.

Any files that contain protected health information that might be created during the course of the study will be stored on department servers. The PI and project manager will coordinate with the Department IT staff to control access to these folders.

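### The patient arm is assigned on entry to Qualtrics, before the T0 survey; assigning at the end of T0 would avoid a small dilution of hypothesis 1.1 and some missing covariates

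*Combined protocol and SAP*

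**What the plan says.** Section 6.0 (Patients) states: "When the participant enters Qualtrics, this will trigger Qualtrics to assign them to the Control group" or to the intervention group. The trigger is entry to the survey platform.

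Section 7.2 gives the order of events after that: "When the participant clicks the link, they will be taken to Qualtrics and the baseline survey (T0"). The length is also given: "The baseline (T0) and post-intervention (T1) surveys are planned to take about 10 minutes each to complete". Exposure comes later: "After the participant completes T0, Qualtrics is programmed to stream the appropriate decision aid for that participant". T1 follows the decision aid.

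Section 10.0 sets the analysis principle: "Primary analysis of outcomes will employ an intent-to-treat analysis". Its check on dropout names patients who do not complete T1 and/or T2; T0 is not mentioned. Section 3.1 takes uptake from the EHR within six months of enrollment. Section 11.0 promises a CONSORT diagram that accounts for missing data.

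Two statements limit the problem. Before the link is sent, the research assistant collects the ACN risk factors by phone (section 7.2): "This involves confirming gender, age, and family history of colorectal cancer", followed by smoking history and waist size. Section 12.0 adds: "REDCap and Qualtrics surveys will allow participants to pass over questions and still continue through the remainder of the questions".

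**The concern.** Assignment comes before T0 and exposure comes after it. The documents describe nothing before the decision aid that differs by patient arm, and they give no reason for assigning early. The interval of about 10 minutes can only create randomised patients with no exposure to either decision aid.

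Two things are at stake. First, because uptake comes from the EHR, a T0 stopper has an obtainable outcome and belongs in the intent-to-treat comparison, where the patient message cannot have had any effect on them. Second, income, education, numeracy, literacy and earlier screening recommendations come from T0 (section 3.2). Section 10.0 adjusts for baseline characteristics that differ at p<.20 but states no method for missing covariates. If such a characteristic enters the logistic model, a complete-case fit would drop T0 stoppers, contrary to intent-to-treat.

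**Working it through.** **Sequence.** Sections 6.0 and 7.2 together give: link opened → arm assigned → T0 (about 10 minutes) → decision aid → T1. Stopping between the second and fourth steps leaves a patient who is assigned and unexposed.

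**Inputs from section 10.0.** Uptake 30% vs 40% (odds ratio 1.55), two-sided 0.05, power 80%, 732 before inflation, ICC 0.05, 8 patients per provider, attrition 10%, final 1100.

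**Reproducing the plan's figure.** Wald test on the log odds ratio with two equal margins:

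N = 2(1.960 + 0.842)² × [1/(0.3×0.7) + 1/(0.4×0.6)] / (ln OR)²

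This gives 718 with the exact odds ratio of 1.556 and about 730 with the rounded 1.55; the plan states 732. The design effect is 1 + (8 − 1)×0.05 = 1.35. Then 732 × 1.35 = 988.2, and 988.2/0.9 = 1098, against the stated 1100. The chain reproduces.

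**Dilution.** Let x be the share of randomised patients who stop during T0. The documents do not give x; 3% to 10% is an assumption. Stoppers see no decision aid in either arm, so their expected difference is zero, and the contrast becomes 10 × (1 − x) points with control uptake held at 30%.

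**Power.** With p0 = 0.30, p1 = 0.30 + 0.10(1 − x) and n = N/(2 × design effect) per arm:

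- b = ln[p1/(1 − p1)] − ln[p0/(1 − p0)]
- SE = √{[1/(p0(1 − p0)) + 1/(p1(1 − p1))]/n}
- power = Φ(b/SE − 1.960)

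The analysed number is 1100 × 0.9 = 990. With design effect 1.35, n = 366.7; with 1.0, n = 495. Example at 1.35: for x = 0, b = 0.442, SE = 0.156, b/SE = 2.83, power 80.8%; for x = 0.10, b = 0.400, SE = 0.156, b/SE = 2.56, power 72.5%.

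| x (assumed) | Effect, points | Power, design effect 1.0 | Power, design effect 1.35 |
|---|---|---|---|
| 0 | 10.0 | 90.8% | 80.8% |
| 3% | 9.7 | 89.2% | 78.5% |
| 5% | 9.5 | 87.9% | 76.9% |
| 10% | 9.0 | 84.4% | 72.5% |

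The 1.0 column is nearer the truth for hypothesis 1.1. Qualtrics assigns the patient message to individuals within provider, so between-provider variance largely cancels. The plan applies 1.35 to both factors, which is conservative for this one.

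**Sensitivity to the analysed number.** If T0 stoppers are kept through the EHR, they are not attrition. With all 1100 analysed and 1.35 retained, power is 82.6% at 3%, 81.1% at 5% and 76.9% at 10%.

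**The case against.** The strongest reply is that nothing is biased and the loss is small. T0 is the same in both arms, assignment is automated, and staff who deal with patients are blinded to the patient arm, so stopping in T0 should not depend on arm. That stands.

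A reader might infer that the trial drops below its planned 80% power. The documents do not support this for hypothesis 1.1. With a design effect near 1.0, power stays above 80% across the assumed range. The drop from 81% to 72.5% needs both a design effect meant for the provider factor and removal of 10% attrition from a set whose EHR outcomes can still be obtained.

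A reader might also infer that T0 stoppers have no baseline at all. They do not: age, gender, family history, smoking and waist size are already held. What is missing is the T0 survey data.

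The stopping rate may be low. Participants have already been through a recruitment call and given risk-factor data, and a research assistant can help by phone or at the clinic. The documents do not say whether a link can be reopened to finish T0. A fear that non-starters would be dropped after the fact is speculation, given the commitments to intent-to-treat and to a full CONSORT account.

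None of this is a reason to assign before T0. It limits the size of the gain.

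**Conclusion.** The point holds as an inexpensive improvement to the design. On the text of sections 6.0 and 7.2, patients who stop during T0 are randomised on the patient factor, unexposed to a decision aid and incomplete on T0. Under intent-to-treat with EHR uptake they dilute hypothesis 1.1 in proportion to their share: 9.7 to 9.0 points instead of 10 if 3% to 10% stop. With 990 analysed, the cost is roughly 2 to 6 points of power with no design effect, and 2 to 8 points at 1.35.

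This rests on an assumed stopping rate, on no effect of the patient message in those who never reach the decision aid, and on stoppers staying in the analysis. The finding is one of efficiency and missing covariates; it does not show that the planned comparison is biased. The provider factor is randomised separately, and the provider message may still be sent for a T0 stopper, so the plan also needs to say where such patients stand for hypothesis 1.2.

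**What to change.** 1. In section 6.0, place the Qualtrics randomiser immediately after the last T0 item and before the decision aid streams. Suggested wording: *Completion of T0 triggers assignment.*
2. In the CONSORT diagram (section 11.0), report patients who consent or open the link but do not finish T0 as losses before patient randomisation.
3. In section 10.0, state that the analysis set for both factors (hypotheses 1.1 and 1.2) starts at completion of T0, and count the 1100 from there. For 1.2 this is safe where T0 is finished before the provider message goes out, since patients are blinded to provider assignment.
4. Keep the six-month uptake window running from enrollment, as the plan defines it, and state which event counts as enrollment.

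The cost is a survey-flow edit, a few sentences and slightly more consents to reach 1100. No bias is introduced, because completing T0 cannot depend on a patient arm not yet assigned. The change does not prevent skipped T0 items, and it does not cover patients who stop during the decision aid or T1.
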